32. **Follow Up:** Patients should be evaluated up to 60 days for safety (SAEs) after last dose of study treatment. Refer to the protocol for specific guidelines. Patients continuing to experience drug related toxicity following discontinuation of study treatment will continue to be followed at least every 4 weeks until resolution or determination, in the clinical judgment of the Investigator, that no further improvement is expected. PK and immunogenicity samples should be collected as described in the PK and Immunogenicity **ASSESSMENTS** Section in SOA ([Table 2](#)).

Patients whose disease has not progressed at the end of treatment will enter into disease follow up. During this follow up period, patients will have disease assessments performed every 8 weeks (± 7 days). Once patients have exhibited disease progression or began a new anticancer therapy, or 6-month follow-up from the date of the last dose of the last enrolled patient, whichever occurs first, they will be withdrawn from the study. See [Section 4.3](#) for guidelines on contraception during this period.

Legend (X) = optional activity to be executed only if applicable; ADA= anti-drug antibodies; AE= adverse event; C=cycle; CRF= case report form; ECG= electrocardiogram; D=day; irRC= Immune-Related Response Criteria; PK=Pharmacokinetics;

TABLE OF CONTENTS

LIST OF TABLES	29
LIST OF FIGURES	29
APPENDICES	30
1. INTRODUCTION	31
1.1. Mechanism of Action/Indication	31
1.2. Background and Rationale	31
1.2.1. 4-1BB Target Biology and Mechanism of Action	31
1.2.2. Preclinical Profile of PF-05082566	32
1.2.2.1. In Vitro PF-05082566 Data	32
1.2.2.2. In Vivo Data: Functional Activity of PF-05082566	33
1.2.2.3. Preclinical Anti-Tumor Activity of PF-05082566	34
1.2.2.4. Preclinical Pharmacokinetics of PF-05082566	34
1.2.2.5. Pharmacokinetics and Pharmacodynamics Relationship of PF-05082566	34
1.2.2.6. Preclinical Toxicology of PF-05082566	35
1.2.3. Clinical Safety of PF-05082566	35
1.2.4. Clinical Efficacy of PF-05082566	38
1.2.4.1. Pharmacokinetics of PF-05082566 in Humans	39
1.2.4.2. Immunogenicity of PF-05082566	39
1.2.5. Mogamulizumab	40
1.2.5.1. Clinical Safety Data for Mogamulizumab	41
1.2.5.2. Pharmacokinetics of Mogamulizumab	43
1.2.5.3. Immunogenicity of Mogamulizumab	43
CCl	44
1.2.6. Study Rationale	44
2. STUDY OBJECTIVES AND ENDPOINTS	46
2.1. Objectives	46
2.2. Endpoints	47
3. STUDY DESIGN	48
3.1. Study Overview	48
3.1.1. Dose-Finding portion	48

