19. **Adverse Event (AE) Assessments:** Adverse events should be documented and recorded at each visit using NCI CTCAE version 4.03. Patients must be followed for AEs for 28 days after the last treatment administration or until all drug related toxicities have resolved, whichever is later; or earlier than 28 days should the patient commence another anticancer therapy in the meantime. For SAEs, the active reporting period begins from the time that the patient provides informed consent, through and including 60 calendar days after the last administration of the investigational products and before initiation of a new anti-cancer treatment. SAEs experienced by a patient after the active reporting period has ended should be reported to the Sponsor if the Investigator becomes aware of them; at a minimum, all SAEs that the Investigator believes have at least a reasonable possibility of being related to study drug are to be reported to the Sponsor. Pregnancy or breast feeding that occur during the trial, within 60 days of discontinuing treatment with mogamulizumab, or within 60 days after the cessation of PF-05082566 if the patient begins a new anticancer therapy, whichever is earlier, should be reported as stated in (see [Section 8.10](#), Exposure During Pregnancy for details).

20. **Concomitant Medications:** Concomitant medications will be recorded from 28 days prior to the start of study treatment and up to 28 days after the last dose of study treatment.

21. **Blood for PF-05082566 Pharmacokinetics:** Blood samples (2 mL whole blood at each time point) will be collected as follows:
Dose-finding cohorts: Cycles 1- 4 on Day 1 at pre-dose and at the end of PF-05082566 infusion; Cycle 5 on Day 1 at pre-dose, at the end of PF-05082566 infusion, and at 2, 6, 168 hrs. (Day 8) and 336 hrs. (Day 15) after the start of PF-05082566 infusion. Day 1 at pre-dose of Cycles 8, 12, 16, 20, 24 and at EOT. See [Section 7.3.1](#).
Expansion cohorts: the same PK schedule foreseen in the dose-finding portion will be followed for at least 10 patients in total from all expansion cohorts. For all other patients in the expansion cohorts, blood for PK will be taken on Cycle 1 Day 1 (at pre-dose and at the end of PF-05082566 infusion), Day 1 at pre-dose of Cycles 3, 5, 8, 12, 16, 20, 24 and at EOT. Timing of sampling may be modified based on emerging safety/PK data. See [Section 7.3.1](#).

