6.3. Follow-up Visit

For follow-up procedures, see [Schedule of Activities](#) and [ASSESSMENTS](#) Sections.

Patients continuing to experience treatment-related toxicity following discontinuation of study treatment will continue to be followed at least every 4 weeks until resolution or determination, in the clinical judgment of the Investigator, that no further improvement is expected.

Only those patients whose disease has not progressed at the end of treatment will enter into disease follow-up. During this follow-up period, patients will have disease assessments performed every 8 weeks \pm 7 days. Once patients have exhibited disease progression or began a new anti-cancer therapy (not including radiotherapy to a non-target tumor lesion), whichever occurs first, the date of progression or that of the new anticancer therapy initiation will be recorded on the appropriate CRF page, and the patients will be withdrawn from the study. No further data will be collected from these patients.

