8.2. Reporting Period

For SAEs, the active reporting period to Pfizer or its designated representative begins from the time that the patient provides informed consent, which is obtained prior to the patient's participation in the study, ie, prior to undergoing any study-related procedure and/or receiving investigational product, through and including 60 calendar days after the last administration of the investigational product. SAEs occurring to a patient after the active reporting period has ended should be reported to the Sponsor if the investigator becomes aware of them; at a minimum, all SAEs that the investigator believes have at least a reasonable possibility of being related to investigational product are to be reported to the Sponsor.

AEs (serious and nonserious) should be recorded on the CRF from the time the patient has taken at least 1 dose of investigational product through the patient's last visit.

If a patient begins a new anticancer therapy, the AE reporting period for nonserious AEs ends at the time the new treatment is started. Death must be reported if it occurs during the SAE reporting period after the last dose of investigational product, irrespective of any intervening treatment.

Pregnancy or breast feeding that occur during the trial, within 60 calendar days of discontinuing treatment with mogamulizumab, or within 60 days after the cessation of PF-05082566 if the patient begins a new anticancer therapy, whichever is earlier, should be reported as in [Section 8.10](#) (Exposure During Pregnancy).

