6.6.2. Deaths

The frequency (number and percentage) of patients in the safety analysis set who died and who died within 30 days and within 60 days after last dose of study treatment as well as the cause of death, will be tabulated based on information from the 'Notice of Death' eCRFs, by treatment group.

- All deaths (within 30 days, and within 60 days);
- Deaths (within 30 days, and within 60 days) after last dose of study treatment;
- Cause of Death:
 - Disease under study;
 - Study treatment toxicity;
 - Unknown;
 - Other.

In addition, date and cause of death will be provided in individual patient data listing together with selected dosing information (study treatment received, date of first / last administration, dose) and will include the following information:

- AEs with fatal outcome (list preferred terms of AEs with outcome=Fatal, as well as AEs of Grade 5);
- Flag for death \leq 30 days and 31-60 days after last dose of study treatment.

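### Protocol footnote 19 and Section 8.2 disagree on whether active SAE reporting continues once a new anti-cancer therapy starts within 60 days of the last dose

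*Protocol*

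**What the plan says.** Four places in the protocol, and one in the SAP, bear on a patient who starts another anti-cancer therapy within 60 days of the last dose.

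- **Protocol, Schedule of Activities, footnote 19.** The active SAE period runs from consent "through and including 60 calendar days after the last administration of the investigational products and before initiation of a new anti-cancer treatment". After it closes, reporting is passive: "SAEs experienced by a patient after the active reporting period has ended should be reported to the Sponsor if the Investigator becomes aware of them". The footnote adds that SAEs with a reasonable possibility of relation to study drug are to be reported as a minimum.
- **Protocol, Section 8.2.** The active SAE period runs "through and including 60 calendar days after the last administration of the investigational product", with no cut at new therapy. It then says: "If a patient begins a new anticancer therapy, the AE reporting period for nonserious AEs ends at the time the new treatment is started". On deaths: "Death must be reported if it occurs during the SAE reporting period after the last dose of investigational product, irrespective of any intervening treatment". The passive fallback matches footnote 19.
- **Protocol, Section 6.3.** This paragraph covers only patients who had not progressed at end of treatment and so entered disease follow-up. At progression or new therapy, that date is recorded and "the patients will be withdrawn from the study. No further data will be collected from these patients". No exception is made for SAEs or deaths.
- **Protocol, footnote 32 and Section 6.4.** Footnote 32 asks for SAE evaluation up to 60 days after the last dose, then withdraws disease follow-up patients at progression or new therapy. Section 6.4 lists another anti-cancer therapy as a possible reason for leaving study follow-up.
- **SAP, Section 6.6.2.** It tabulates patients "who died within 30 days and within 60 days after last dose of study treatment" and flags deaths on days 31 to 60. It states no cut at new therapy.

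**The concern.** The same patient on the same day is inside the active SAE period under one section and outside it under another. All of this is current text. The footnote 19 clause cannot be read as a stray reference to nonserious events, because the same footnote gives general AE follow-up its own, separate cut at new therapy.

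The overall safety profile is a secondary objective, and the protocol states that no nonclinical toxicology was done on the combination. Patients with refractory tumours may well move to another therapy soon after stopping. Their serious events in the rest of the 60 days may not be actively sought, and some deaths that the SAP intends to count may not be recorded.

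**Working it through.** The plan states no figure to reproduce, so the check is to set the rules side by side for the two kinds of patient and then size the disputed window.

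**Patient A: progressed on treatment, then starts new therapy on day t < 60.** This patient does not enter disease follow-up, so the data stop in Section 6.3 does not apply.

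| Source | Active SAE reporting after day t | Deaths to day 60 |
|---|---|---|
| Footnote 19 | Ends; passive reporting remains | No separate rule |
| Section 8.2 | Continues to day 60 | Required whatever treatment intervenes |

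There are two rules, in direct conflict on SAEs. On deaths Section 8.2 is explicit, and Section 8.6 also makes a fatal malignancy outcome in the safety reporting period an SAE.

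**Patient B: stopped without progression, entered disease follow-up, then progresses or starts new therapy before day 60.**

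| Source | SAEs after that date | Deaths after that date |
|---|---|---|
| Footnote 19 (new therapy only) | Passive reporting | No separate rule |
| Section 8.2 | Active to day 60 | Required |
| Section 6.3 | No data collected | No data collected |
| Footnote 32 | 60-day evaluation, but patient withdrawn | Not stated |

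Here Section 6.3 adds a third rule, and the 60-day death count in SAP Section 6.6.2 is exposed.

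**Size of the disputed window.** With new therapy on day t, Section 8.2 gives 60 - t further days of active SAE reporting and footnote 19 gives none. The documents give no t, so these values are assumed:

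- t = 14: 60 - 14 = 46 days (46/60 = 77% of the window)
- t = 28: 60 - 28 = 32 days (32/60 = 53%)
- t = 45: 60 - 45 = 15 days (15/60 = 25%)

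**What reaches the analysis.** SAP Section 5.2.7 ends the on-treatment period at the earlier of 30 days after the last dose and the day before new anti-cancer drug therapy. Later safety data are listed and flagged but not summarised. An SAE after a new drug starts is therefore outside the SAE summary tables under either protocol rule, and the conflict changes only whether it appears in the Section 6.6.3 listing. The SAP definition names drug therapy; surgery or radiotherapy does not close that period, and this point does not rest on such cases. The death table is different, because it runs to day 60 with no stated cut.

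**MTD.** The model uses DLTs in the first two cycles that are attributable to study drug. Related SAEs stay reportable under footnote 19 and Section 8.2 alike, and both cut nonserious AEs at new therapy.

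**The case against.** The strongest reply is that little is lost in practice. The fallback keeps every SAE the investigator learns of, and related ones at a minimum. Continuing drug-related toxicity is followed at least every 4 weeks after discontinuation. Section 8.2 protects deaths explicitly. The Schedule of Activities calls itself an overview and footnote 32 refers the reader to the protocol for guidance, which leans towards Section 8.2.

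Most of that stands, and it limits the harm. It does not remove the conflict: no text gives Section 8.2 precedence, and Section 6.3 itself sends sites to the Schedule of Activities for follow-up procedures. What remains exposed is SAEs no longer actively sought, mainly those thought unrelated or not yet known to the site.

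Four stronger readings are tempting but unsupported:

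- *Late SAEs will be captured at some sites and not at others.* This is a reasonable fear, but the documents do not say which section sites follow.
- *Patients who leave for progression lose all later data and deaths.* Section 6.3 covers only those not progressed at end of treatment.
- *The MTD or the SAE tables are compromised.* The DLT definition and SAP Section 5.2.7 do not support this.
- *Residual drug shows how much is missed.* A 10-day half-life leaves 2^-(28/10) = 14% of PF-05082566 at 28 days after its own dose. If the last study dose is mogamulizumab on Day 15, PF-05082566 is 14 + 28 = 42 days old by then, leaving 2^-(42/10) = 5%. Neither figure gives a number of events.

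**Conclusion.** The contradiction is real and the text is wrong as written. For any patient starting new therapy on day t < 60, footnote 19 and Section 8.2 differ by 60 - t days of active SAE reporting. For the disease follow-up subset, Section 6.3 goes further and may leave the 60-day death count incomplete. The consequence is confined to the SAE listings and that death count.

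The day counts rest on assumed switch times. The number of patients or SAEs affected cannot be derived from the documents, so the finding should be stated as events that may be missed. It is a consistency defect with a modest effect, worth correcting because the correction is cheap.

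**What to change.** Reconcile the text to one rule consistent with Section 8.2:

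1. In footnote 19, delete the final condition of the SAE sentence that closes active reporting when a new anti-cancer treatment begins.
2. In Section 6.3, footnote 32 and Section 6.4, state that withdrawal at progression or new therapy ends tumour assessments only, and that SAE and death collection continues through 60 days after the last dose. Refusal of follow-up and withdrawal of consent keep their present effect.
3. Leave the SAP as it is. Section 6.6.3 already flags SAEs with onset outside the on-treatment period, and new drug therapy closes that period.

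The cost is wording in an amendment or clarification letter. Added site work is small, because footnote 32 already asks for SAE evaluation to 60 days. The downside is that some late SAEs will be confounded by the new therapy; the existing flag and the recorded start date of that therapy let a reader see which.

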11. Male and female patients of childbearing potential and at risk for pregnancy must agree to use two (2) highly effective methods of contraception throughout the study and for 60 days after the last dose of assigned study treatment.

12. Female patients who are not of childbearing potential (ie, meet at least one of the following criteria):

- Have undergone a documented hysterectomy and/or bilateral oophorectomy;
- Have medically confirmed ovarian failure; **OR**
- Achieved post-menopausal status, defined as follows: cessation of regular menses for at least 12 consecutive months with no alternative pathological or physiological cause; and have a serum follicle stimulating hormone (FSH) level within the laboratory's reference range for postmenopausal women.

13. Evidence of a personally signed and dated informed consent document indicating that the patient has been informed of all pertinent aspects of the study.

14. Patients who are willing and able to comply with scheduled visits, treatment plans, laboratory tests and other procedures.

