4.3. Lifestyle Guidelines

In this study, patients of childbearing potential will receive PF-05082566 and mogamulizumab, compounds for which the teratogenic risk in human is currently unknown. Two (2) methods of highly effective contraception must be used throughout the study and continued for at least 60 days after the last dose. The investigator or his/her designee, in consultation with the patient, will select two appropriate methods of contraception for the individual patient from the list of permitted contraception methods (see below) and instruct the patient in their consistent and correct use.

Patients need to affirm that they meet at least 2 of the selected methods of contraception. The investigator or his/her designee will discuss with the patient the need to use highly effective contraception consistently and correctly according to the [Schedule of Activities](#) and document such conversation in the patient's chart. In addition, the investigator or his/her designee will instruct the patient to call immediately if a selected contraception method is discontinued or if pregnancy is known or suspected.

Highly effective methods of contraception are those that, alone or in combination, result in a failure rate of less than 1% per year when used consistently and correctly (ie, perfect use) and include:

1. Established use of oral, inserted, injected or implanted hormonal methods of contraception is allowed provided the patient plans to remain on the same treatment throughout the entire study and has been using that hormonal contraceptive for an adequate period of time to ensure effectiveness.
2. Correctly placed copper-containing intrauterine device (IUD).
3. Male condom or female condom used WITH a spermicide (ie, foam, gel, film, cream, or suppository). For countries where spermicide is not available or condom plus spermicide is not accepted as highly effective contraception, this option is not appropriate.
4. Male sterilization with absence of sperm in the post-vasectomy ejaculate.
5. Bilateral tubal ligation or bilateral salpingectomy or bilateral tubal occlusive procedure (provided that occlusion has been confirmed in accordance with the device's label).

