8.10. Exposure During Pregnancy

For unapproved/unlicensed products and for marketed products, an exposure during pregnancy occurs if:

1. A female becomes, or is found to be, pregnant either while receiving or having been exposed (eg, because of treatment or environmental exposure) to the investigational product; or the female becomes, or is found to be pregnant after discontinuing and/or being exposed to the investigational product;

An example of environmental exposure would be a case involving direct contact with a Pfizer product in a pregnant woman (eg, a nurse reports that she is pregnant and has been exposed to chemotherapeutic products).

2. A male has been exposed (eg, because of treatment or environmental exposure) to the investigational product prior to or around the time of conception and/or is exposed during his partner's pregnancy.

If a study patient or study patient's partner becomes or is found to be pregnant during the study patient's treatment with the investigational product, the investigator must submit this information to the Pfizer drug safety unit on a Serious Adverse Event (SAE) Report Form and Exposure During Pregnancy (EDP) supplemental form, regardless of whether an SAE has occurred. In addition, the investigator must submit information regarding environmental exposure to a Pfizer product in a pregnant woman (eg, a patient reports that she is pregnant and has been exposed to a cytotoxic product by inhalation or spillage) using the EDP supplemental form. This must be done irrespective of whether an AE has occurred and within 24 hours of awareness of the exposure. The information submitted should include the anticipated date of delivery (see below for information related to termination of pregnancy).

Follow-up is conducted to obtain general information on the pregnancy and its outcome for all EDP reports with an unknown outcome. The investigator will follow the pregnancy until completion or until pregnancy termination and notify Pfizer of the outcome as a follow-up to the initial EDP supplemental form. In the case of a live birth, the structural integrity of the neonate can be assessed at the time of birth. In the event of a termination, the reason(s) for the termination should be specified and, if clinically possible, the structural integrity of the terminated fetus should be assessed by gross visual inspection (unless preprocedure test findings are conclusive for a congenital anomaly and the findings are reported).

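### Pregnancy reporting is timed from each drug separately, so for patients who have left the study it can end before the 60-day contraception period does

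*Protocol*

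**What the plan says.** The reporting rule appears twice in the Protocol with essentially the same wording. Schedule of Activities footnote 19 opens with "Pregnancy or breast feeding that occur during the trial, within 60 days of discontinuing treatment with mogamulizumab" and continues "or within 60 days after the cessation of PF-05082566 if the patient begins a new anticancer therapy, whichever is earlier, should be reported" under Section 8.10. Section 8.2 (Reporting Period) has "within 60 calendar days of discontinuing treatment with mogamulizumab, or within 60 days after the cessation of PF-05082566", followed by the same new-therapy condition and the same earlier-of qualifier.

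The contraception rule is anchored differently. Section 4.1, criterion 11, requires "highly effective methods of contraception throughout the study and for 60 days after the last dose of assigned study treatment". Section 4.3 says two methods "must be used throughout the study and continued for at least 60 days after the last dose". Section 5.1 states that study drug or study treatment means both agents, so this clock starts at whichever drug was given last.

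Section 8.10 defines exposure during pregnancy without a time limit and includes the case where "the female becomes, or is found to be pregnant after discontinuing and/or being exposed to the investigational product". Its submission sentence, however, covers only a pregnancy in the patient or partner that arises or is found while the patient is on treatment.

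**The concern.** The post-trial reporting period has two dated limbs, each tied to one drug. The PF-05082566 limb applies only if a new anticancer therapy begins. Contraception has a single clock that starts at the last dose of the combination. When the two drugs do not end on the same day, the clocks can separate, and the earlier-of qualifier pushes towards the shorter one.

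The limb covering events during the trial does not always fill the gap. Footnote 32 and Section 6.3 withdraw patients from the study at progression or new anticancer therapy. Section 6.3 adds that no further data are then collected from them.

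What is at stake is safety information. Section 7.1.1 says PF-05082566 has not been characterized for reproductive toxicology and that no human data exist for mogamulizumab. A pregnancy inside the protocol's own contraception period could go unreported and unfollowed. No efficacy or DLT analysis is affected.

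**Working it through.** The plan states no figure to reproduce; this is calendar arithmetic.

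**Inputs**
- PF-05082566 is given on Day 1 of each 28-day cycle (footnote 16).
- Mogamulizumab is given on Days 1, 8, 15 and 22 of Cycle 1, then on Days 1 and 15 (footnote 17).
- Reporting limbs are 60 days each (footnote 19, Section 8.2). Contraception is 60 days (Sections 4.1 and 4.3).
- Assumption: stopping a drug is dated from its last dose, since the documents do not define it otherwise.
- The patient is off study, so the limb for events during the trial no longer applies.

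**Formulas**
- Study day = 28 × (cycle − 1) + day.
- Contraception ends = later of (last PF-05082566, last mogamulizumab) + 60.
- Without a new therapy, reporting closes = last mogamulizumab + 60, the only dated limb.
- With a new therapy, spanning reading (the qualifier compares both limbs): reporting closes = earlier of (last mogamulizumab + 60, last PF-05082566 + 60).
- With a new therapy, narrow reading (the qualifier belongs only to the PF-05082566 limb): the mogamulizumab limb stands on its own and runs its full 60 days.
- Shortfall = contraception ends − reporting closes, counting at most the 60 days after the last dose.

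| Last PF-05082566 | Last mogamulizumab | New therapy | Closes (spanning) | Contraception ends | Shortfall, spanning | Shortfall, narrow |
|---|---|---|---|---|---|---|
| C4D1 (day 85) | C4D1 (day 85) | yes or no | 145 | 145 | 0 | 0 |
| C4D1 (85) | C4D15 (99) | no | 159 | 159 | 0 | 0 |
| C4D1 (85) | C4D15 (99) | yes | 145 | 159 | 14 | 0 |
| C1D1 (1) | C1D22 (22) | yes | 61 | 82 | 21 | 0 |
| C2D1 (29) | C3D15 (71) | yes | 89 | 131 | 42 | 0 |
| C2D1 (29) | C4D15 (99) | yes | 89 | 159 | all 60 | 0 |
| C3D1 (57) | C2D15 (43) | no | 103 | 117 | 14 | 14 |
| C4D1 (85) | C2D15 (43) | no | 103 | 145 | 42 | 42 |
| C5D1 (113) | C2D15 (43) | no | 103 | 173 | all 60 | all 60 |

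For the ordinary last cycle with a new therapy, 60 − 14 = 46 days are covered and 14/60 = 23% are not. After Cycle 1 Day 22, 60 − 21 = 39 days are covered and 21/60 = 35% are not.

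In the last row the mogamulizumab limb closes on day 103, ten days before the last dose on day 113, so none of the 60 days is covered. The last three rows do not depend on the qualifier, because without a new therapy there is nothing to compare.

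With the window run from the last dose of either drug, reporting closes when contraception ends and every shortfall is 0.

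**The case against.** The strongest objection is the limb for events during the trial. A patient who has not progressed and starts no new therapy enters disease follow-up and stays on study (footnote 32, Section 6.3), and Table 1 schedules a contraception check at follow-up. This stands: such patients have no gap. A reader might infer that anyone who stops mogamulizumab early loses the whole window. The documents do not support that; the loss is confined to patients who have left the study.

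The second objection concerns the reading. The qualifier can be attached to the PF-05082566 limb alone, and the 14- and 21-day shortfalls then vanish. This also stands. It is wrong to present 14 days as what the rule plainly yields; the sentence is ambiguous and the range is 0 to 14 (or 0 to 21).

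Third, the case with no coverage needs one drug to continue alone for 60 days or more. Section 5.4.8 allows resumption of either or both drugs, and SAP Section 6.5.2.1 tabulates discontinuation separately for each drug. Single-drug continuation is therefore contemplated, but it is not a planned pathway.

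Fourth, other reporting may catch some cases. Footnote 32 has patients evaluated for SAEs up to 60 days after the last dose, and Section 8.10 sends pregnancy outcomes that meet SAE criteria to SAE reporting. This is partial: a pregnancy whose outcome is not an SAE is not caught, and footnote 19 ends active SAE reporting when a new therapy begins. Section 7.1.1 also reports no embryo-fetal signal for mogamulizumab in animals, which lowers the stakes for that drug but not for PF-05082566.

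Finally, contraception and reporting are different obligations, and unequal lengths are not in themselves a contradiction. A reader might infer that footnote 19 contradicts Section 8.10 outright. It conflicts with the open-ended exposure definition there, but the submission sentence in the same section is narrower still, so Section 8.10 also needs attention.

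**Conclusion.** The concern holds in a conditional form. For patients no longer on study, post-trial pregnancy and breastfeeding reporting can close before the 60-day contraception period does, because its limbs are tied to each drug instead of to the last dose of study treatment.

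- New therapy started, spanning reading: 14 days short after an ordinary last cycle and 21 days short after Cycle 1 Day 22. On the narrow reading both are 0.
- Mogamulizumab stopped first, PF-05082566 continued alone, patient off study without a new therapy: short by the interval between the two last doses, up to the full 60 days, on either reading.
- No gap when both drugs end the same day, when mogamulizumab is last and no new therapy starts, or while the patient remains in study follow-up.

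A reader might also infer that the window runs from a single drug. It does not: the sentence names both, and each limb is tied to one. The sizes assume that stopping is dated from each drug's last dose and that withdrawn patients fall outside the limb for events during the trial. Few pregnancies are to be expected in this trial. This is a minor drafting defect in safety capture, worth correcting because the correction is easy.

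**What to change.** Reconcile three places with the contraception period: footnote 19, Section 8.2 and the submission sentence in Section 8.10. The aligned rule would require reporting of pregnancy (including partner pregnancy) or breastfeeding that occurs during the trial or within 60 days after the last dose of either study drug, whichever drug was given last, regardless of any new anticancer therapy. Delete the earlier-of qualifier. Extend the Section 8.10 submission sentence beyond the treatment period to match; otherwise the cross-reference would lead to a duty that stops at the end of treatment.

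The cost is a short text change in three places and a few more days of passive reporting for some patients. Contraception requirements, treatment and all analyses stay as they are.
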